4.10.1 Extent of Exposure

The extent of exposure (days) will be derived as follows for AZD5718 and for dapagliflozin:

$$\begin{aligned} \text{Duration of exposure[AZD5718] (days)} \\ = \text{Date of last dose[AZD5718]} - \text{Date of first dose[AZD5718]} + 1 \end{aligned}$$

$$\begin{aligned} \text{Dur. of exp. to dapagliflozin (days)} \\ = \text{Date of last dose[dapagliflozin]} - \text{Date of first dose[dapagliflozin]} \\ + 1 \end{aligned}$$

The following extent of exposure summaries will be provided separately for AZD5718 and for dapagliflozin:

- A summary of the duration of exposure to treatment (days) and cumulative exposure over time (≥ 1 day, ≥ 28 days, ≥ 57 days, ≥ 85 days, ≥ 120 days), by treatment group.
- Total exposure to study treatment (days) = (min(last dose date, death date) - first dose date + 1) / (365.25)
- Time on study – defined as the time in days from the start date of treatment to the date of last study assessment or the date of withdrawal.

A summary of duration of exposure to treatment (days) will also be presented for the Monotherapy Safety Analysis Set and the Extended Safety Analysis Set with Week 12 flag.

The following summaries will be produced for the Safety Analysis Set, by treatment group:

- Number of and reasons for dose interruptions

4.10.2 Adverse Events

Adverse events will be coded using MedDRA version 23.0 or later.

An AE (classified by preferred term) started during the treatment period will be considered a treatment-emergent adverse event if it was not present prior to the first dose of randomised treatment. An AE that starts more than 7 days after the last dose of study medication will not be counted as a treatment-emergent AE. AEs which worsen after the start of treatment will not be included as a treatment-emergent AE but will be recorded.

Adverse events (and also separately SAEs) will be summarised by study treatment group in incidence summaries by MedDRA SOC and PT. Adverse events will be assigned to the period where they start and will be summarised for the Safety Analysis Set, with selected outputs summarized for the Monotherapy Safety Analysis Set and Extended Safety Analysis Set with Week 12 flag. Serious adverse event collection will begin after the participant signs the informed consent document, and all AE collection will begin after the participant has received the first dose of the study drug. The SAE/AE collection will last until the end of the participant’s follow-up period.

All AEs will be listed and assigned to on/off treatment period as:

- Prior treatment: The SAE occurred before the first administration of study drug. Only applicable for SAEs.
- On treatment: The AE occurred on or after the first administration until 7 days after last dose of AZD5718 and/or dapagliflozin.
- Off treatment: The AE occurred more than 7 days after the last dose of study drug.

The number, percentage and percentage per participant exposure year (PEY) of participants reporting treatment-emergent AEs in each treatment group will be tabulated by SOC and PT; by SOC; by SOC, PT, and relationship to study medication as assessed by the Investigator. If more than one event occurs with the same preferred term for the same participant, the participant will be counted only once for that preferred term using the most severe and most related occurrence for the summarisation by severity and by relationship to the study medication.

The event rate per 100 PEY is defined as:

$$\left(\frac{\text{number of subjects with AE}}{\text{sum of days at risk for AE in treatment period} + 7 \text{ days}} \right) \times 365.25 \times 100$$

The denominator is calculated per participant then summed. The distribution of treatment-emergent AEs by severity and relationship to study medication will be summarized by treatment group.

A summary of AEs in any category will be presented by treatment. The incidence of common ($\geq 5\%$ of participants in any treatment group) treatment-emergent AEs, common treatment-emergent serious AEs, and AEs leading to discontinuation of study medication will be summarized by SOC, PT and treatment group, sorted in decreasing overall (across treatments) frequency. Treatment-emergent AEs with outcome of deaths will also be presented. In addition, all fatal SAEs (ie, events that caused death) will be summarized. For each participant and each AE, the worst intensity recorded will be attributed and used in the by-intensity summaries. Similarly, the worst causality will be attributed and used in the by-causality summaries. Multiple occurrences of a treatment-emergent AE in the same participant will only be counted once overall. Non-serious treatment-emergent AEs occurring in more than 5% of participants will be presented by treatment.

The number and percentage of participants reporting AEs by treatment group, SOC and PT will also be presented for the Monotherapy Safety Analysis Set and the Extended Safety Analysis Set with Week 12 flag.

Listings will be presented of participants with SAEs, AEs leading to discontinuation, and participants who died. A listing will be presented of participants with AEs, detailing whether these are SAEs, AEs leading to discontinuation, or result in death. Listings will include on- and off-treatment categorization.

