8.3 Adverse Events and Serious Adverse Events

The Investigator is responsible for ensuring that all staff involved in the study are familiar with the content of this section.

The definitions of an AE or SAE can be found in [Appendix B](#).

Adverse events will be reported by the participant (or, when appropriate, by a caregiver, surrogate, or the participant's legally authorised representative).

The Investigator and any designees are responsible for detecting, documenting, and recording events that meet the definition of an AE.

8.3.1 Time Period and Frequency for Collecting Adverse Event and Serious Adverse Event Information

Serious AEs will be recorded from time of signature of the ICF and all AEs will be collected after the participant has received the first dose of study drug. The collection of AEs/SAEs will continue throughout the treatment period and including the Follow-up Period.

If the Investigator becomes aware of an SAE with a suspected causal relationship to the study drug that occurs after the end of the clinical study in a participant treated by him or her, the Investigator shall, without undue delay, report the SAE to the Sponsor.

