8.3.2 Follow-up of Adverse Events and Serious Adverse Events

Any AEs that are unresolved at the participant's last AE assessment in the study are followed up by the Investigator for as long as medically indicated, but without further recording in the eCRF. AstraZeneca retains the right to request additional information for any participant with ongoing AE(s)/SAE(s) at the end of the study, if judged necessary.

Adverse Event Variables

The following variables will be collected for each AE:

- AE (verbatim)
- The date and time when the AE started and stopped
- Maximum intensity
- Whether the AE is serious or not
- Investigator causality rating against the study drugs (yes or no)
- Action taken with regard to study drugs
- AE caused participant's withdrawal from study (yes or no)

- Outcome

In addition, the following variables will be collected for SAEs:

- Date AE met criteria for SAE
- Date Investigator became aware of SAE
- AE is serious due to
- Date of hospitalisation
- Date of discharge
- Probable cause of death
- Date of death
- Autopsy performed
- Causality assessment in relation to study procedure(s)
- Causality assessment to other medication

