8.3.5 Adverse Events Based on Examinations and Tests

The results from the Clinical Study Protocol (CSP) mandated laboratory tests and vital signs will be summarised in the Clinical Study Report (CSR).

Deterioration as compared to baseline in CSP-mandated laboratory values and vital signs should therefore only be reported as AEs if they fulfil any of the SAE criteria, are the reason for discontinuation of treatment with the study drug or are considered to be clinically relevant as judged by the Investigator (which may include but not limited to consideration as to whether treatment or non-planned visits were required or other action was taken with the study drug, eg, dose adjustment or drug interruption).

If deterioration in a laboratory value/vital sign is associated with clinical signs and symptoms, the sign or symptom will be reported as an AE and the associated laboratory result/vital sign will be considered as additional information. Wherever possible the reporting Investigator uses the clinical, rather than the laboratory term (eg, anaemia versus low haemoglobin value). In the absence of clinical signs or symptoms, clinically relevant deteriorations in non-mandated parameters should be reported as AE(s).

Any new or aggravated clinically relevant abnormal medical finding at a physical examination as compared with the baseline assessment will be reported as an AE unless unequivocally related to the disease under study.

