9.4.3 Safety

All safety analyses will be performed on the Safety Analysis population.

Adverse events (and also separately SAEs) will be summarised by study treatment group in incidence summaries by MedDRA System Organ Class (SOC) and Preferred Term (PT). All AEs will be listed and assigned to on/off treatment period as:

- Prior treatment: The SAE occurred before the first administration of study drug. Only applicable for SAEs.
- On treatment: The AE occurred on or after the first administration until 7 days after last dose of AZD5718 and/or dapagliflozin.
- Off treatment: The AE occurred more than 7 days after the last dose of study drug.

Adverse events will be assigned to the period where they start. Serious adverse event

collection will begin after the participant signs the informed consent document, and all AE collection will begin after the participant has received the first dose of the study drug. The SAE/AE collection will last until the end of the participant's follow-up period. Adverse events will be coded using the MedDRA by SOC and PT. Specific AEs will be counted once for each participant for calculating rates but will be presented in total in participant listings. In addition, if the same AE occurs multiple times within a particular participant, the highest severity and level of causality will be reported. All treatment emergent AEs will be summarised overall and by deaths and SAEs. Treatment discontinuations due to AEs will be summarised.

Clinical laboratory safety tests including serum chemistry, haematology, coagulation, and urinalysis parameters will be summarised using descriptive statistics at each time point by treatment group. Change from baseline to each post baseline time point in these data will also be summarised, where appropriate. A shift table will be provided for these clinical laboratory parameters as well, where possible.

Vital signs and clinical laboratory data and ECG will be summarised at each time point. Change from baseline to each post baseline time point will also be summarised, where appropriate.

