An AE is the development of any untoward medical occurrence in a participant or clinical study participant administered a medicinal product and which does not necessarily have a causal relationship with this treatment. An AE can therefore be any unfavourable and unintended sign (eg, an abnormal laboratory finding), symptom (for example nausea, chest pain), or disease temporally associated with the use of a medicinal product, whether or not considered related to the medicinal product.

The term AE is used to include both serious and non-serious AEs and can include a deterioration of a pre-existing medical occurrence. An AE may occur at any time, including run-in or washout periods, even if no study drug has been administered.

B 2 Definitions of Serious Adverse Event

An SAE is an AE occurring during any study phase (ie, run-in, treatment, washout, follow-up), that fulfils one or more of the following criteria:

- Results in death
- Is immediately life-threatening
- Requires in participant hospitalisation or prolongation of existing hospitalisation
- Results in persistent or significant disability or incapacity
- Is a congenital abnormality or birth defect
- Is an important medical event that may jeopardise the participant or may require medical treatment to prevent one of the outcomes listed above.

Adverse Events for **malignant tumours** reported during a study should generally be assessed as **Serious** AEs. If no other seriousness criteria apply, the 'Important Medical Event' criterion should be used. In certain situations, however, medical judgement on an individual event basis should be applied to clarify that the malignant tumour event should be assessed and reported as a **non-serious** AE. For example, if the tumour is included as medical history and progression occurs during the study, but the progression does not change treatment and/or prognosis of the malignant tumour, the AE may not fulfil the attributes for being assessed as serious, although reporting of the progression of the malignant tumour as an AE is valid and should occur. Also, some types of malignant tumours, which do not spread remotely after a routine treatment that does not require hospitalisation, may be assessed as non-serious; examples in adults include Stage 1 basal cell carcinoma and Stage 1A1 cervical cancer removed via cone biopsy.

Life-threatening

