	Low	< 90%	Decrease of $\geq 5\%$

BP = blood pressure.

For by-visit summaries, the last non-missing assessment (including repeat assessments) recorded at each applicable scheduled visit will be summarised.

The following summaries will be provided:

- A summary of the observed absolute values and change from baseline in each vital sign parameter by treatment group and time point.
- A summary of key participant information for participants reporting notable changes outside predefined criteria in each vital sign parameter.
- A summary of the number and percentage of participants experiencing notable changes from baseline outside predefined criteria, by vital sign parameter and treatment group.
- A summary of the observed absolute values and change from baseline in each ECG parameter by treatment group and time point. Both pre- and post-investigational medicinal product (IMP) measurements will be presented at each time point.
- A summary of the number and percentage of participants with QTcF intervals exceeding predefined upper limits (as stated in [Table 4](#)).
- A summary of ECG assessment (normal/abnormal [clinically significant, not clinically significant]), baseline versus last observation on treatment. Post-IMP measurement at last observation on treatment will be used.
- A summary of key participant information for participants reporting PCS ECG values outside predefined criteria by treatment group and visit.
- A summary of the number and percentage of participants reporting PCS ECG values outside predefined criteria, by ECG parameter and treatment group.

By-participant listings of vital sign parameters, abnormal ECG results, and weight, height, and BMI will also be provided.

Any new or aggravated clinically relevant abnormal medical finding at a physical examination as compared with the baseline assessment will be reported as an AE unless unequivocally related to the disease under study.

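### SAP 4.10.2 denies treatment-emergent status to AEs that worsen, so a reported on-treatment deterioration under the same preferred term can be missing from the TEAE tables

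*SAP*

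**What the plan says.** SAP 4.10.2 sets three conditions for a TEAE. The event, classified by preferred term, must start in the treatment period. It must not have been there before the first randomised dose. It must not start later than 7 days after the last dose. A further sentence then removes worsening: "AEs which worsen after the start of treatment will not be included as a treatment-emergent AE but will be recorded".

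The surrounding rules are wider:

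- Protocol Appendix B 1 says that an AE "can include a deterioration of a pre-existing medical occurrence".
- Protocol 8.3.5 says that an "aggravated clinically relevant abnormal medical finding at a physical examination as compared with the baseline assessment will be reported as an AE", unless it is plainly due to the disease being studied. SAP 4.10.5 repeats this for a finding that is new or worse when "compared with the baseline assessment will be reported as an AE unless unequivocally related to the disease under study".
- Protocol 9.4.3 defines the on-treatment category, and SAP 4.10.2 repeats it: "The AE occurred on or after the first administration until 7 days after last dose of AZD5718 and/or dapagliflozin".
- Protocol 9.4.3 promises: "All treatment emergent AEs will be summarised overall and by deaths and SAEs". It does not define the term.
- On collection, Protocol 8.3.1 says that "all AEs will be collected after the participant has received the first dose of study drug". Only SAEs are recorded from consent.
- Protocol 8.3.2 collects "Maximum intensity" for each AE. SAP 4.10.2 uses the worst recorded intensity in its by-intensity summaries.

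**The concern.** A deterioration that the protocol requires to be reported, and that both documents place in the on-treatment category, can fail the SAP's TEAE rule. Most of the detailed safety tables rest on that rule:

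- TEAEs by system organ class and preferred term, by relationship, by severity, and per participant exposure year;
- common TEAEs and common serious TEAEs;
- non-serious TEAEs in more than 5% of participants;
- TEAEs with outcome of death, including the Monotherapy and Extended set versions (SAP 4.10.3);
- the interim TEAE tables, including TEAEs leading to hospitalisation (SAP Appendix B.3, which gives no definition of its own).

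One report could then disagree with itself. A fatal worsening could be counted among all fatal SAEs but not among TEAEs with outcome of death. Safety and tolerability is a stated secondary objective, so the rule should be one that two programmers would apply in the same way.

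**Working it through.** The plan states no figure to reproduce. The check traces four kinds of deterioration through SAP 4.10.2.

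1. **SAE between consent and first dose that worsens on treatment, same preferred term.** It was present before first dose and it worsened, so it fails both sentences. If the worsening has its own record starting after first dose, that record is on treatment but not a TEAE. This is the clear loss.
2. **Medical-history condition that worsens and is reported as an AE, same preferred term.** The result depends on what counts as present before first dose. Non-serious AEs are not collected then, so the comparator is either the pre-dose SAEs alone or those plus medical history. SAP 4.6 codes medical history in MedDRA, which makes matching possible, but no section says that it is done. With history as comparator the event is lost. Without it, the event is a new AE record and passes the first sentence.
3. **Deterioration coded to a preferred term not seen before dosing.** It passes the first sentence and still counts.
4. **AE that starts on treatment and later becomes more severe.** The first sentence makes it a TEAE, and the worst-intensity rule grades it at its maximum. The worsening sentence is not limited to events present before dosing, so read literally it removes the same event. The two rules conflict.

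**Scale only, not an estimate.** The documents give no AE rates, so neither the number of events lost nor any difference between arms can be derived. Assume equal arms and all randomised participants dosed.

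- *Final analysis* (613 randomised, SAP 4.14): 613/4 = 153.25, about 153 per arm. One reclassified participant moves a term by 1/153 = 0.65 percentage points. The cut-off for common TEAEs (at least 5% in any arm) is 0.05 × 153 = 7.65, so 8 participants (8/153 = 5.2%; 7/153 = 4.6%).
- *Interim* (first 240 randomised, SAP Appendix B.1): 240/4 = 60 per arm. One participant is 1/60 = 1.67 points. The cut-off is 0.05 × 60 = 3 participants (3/60 = 5.0%; 2/60 = 3.3%).
- *Interim sensitivity:* Appendix B.1 ties 240 to about 200 completers, but SAP 4.9.1.5 and 4.12 now say about 211. Scaling gives 240 × 211/200 = 253.2, about 63 per arm. The cut-off becomes 0.05 × 63 = 3.15, so 4 participants (3/63 = 4.8%).

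One reclassified participant removes a term from the common table only if an arm sits exactly at the cut-off and no other arm reaches 5%.

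**The case against.** The strongest reply is that the sentence has a harmless meaning: worsening of an AE already on record does not create a second TEAE. That would fit the rules that count a preferred term once per participant at its worst intensity. The reading is possible and may be what was meant. It is not what the sentence says, because the sentence refuses TEAE status to the AE itself.

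The second reply is that little is lost, and much of it stands. In the SAP's own categories the only AEs before first dose are SAEs, so the certain loss is small. The events stay in the listings with their on/off-treatment category. They also stay in the AE and SAE incidence summaries, the summary of all fatal SAEs and the summary of AEs leading to discontinuation, none of which is worded as TEAE-only. Laboratory shift tables and the notable vital-sign and ECG criteria capture deterioration whatever its TEAE status. These outputs are not full substitutes, because the relationship, severity and exposure-year tables are specified for TEAEs. The Safety Analysis Set also runs to the end of follow-up (SAP 4.5.1), so an unrestricted table can include events later than 7 days after last dose.

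A reader might infer three stronger things that the documents do not support:

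- *That the SAP breaches the protocol's TEAE definition.* The protocol has none.
- *That every worsening of a pre-existing comorbidity disappears.* That needs medical history as the comparator, which is not stated.
- *That a harm is hidden or an arm favoured.* The rule is the same in all arms, no event data are given, and SAP 4.12.1 reports termination for lack of efficacy with no safety concerns.

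**Conclusion.** The point holds as a defect in the definition. The TEAE rule in SAP 4.10.2 is narrower than the AE and on-treatment definitions beside it. Followed literally, it can under-count TEAEs in the final and interim tables. The loss is clear for worsened pre-dose SAEs, conditional for medical-history conditions, and absent where the deterioration is coded to a new preferred term. For AEs that start on treatment, the sentence contradicts the worst-intensity rule.

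The size is unknown. The conclusion assumes that a worsening is reported as an AE, as the protocol provides. How the eCRF records a worsening cannot be seen from these documents. Since other outputs still carry the events, this is a correction that should be made, not a threat to the safety conclusions as a whole.

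**What to change.** Replace the paragraph in SAP 4.10.2 as follows:

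- Delete the worsening sentence.
- Define a TEAE as an AE that starts, or is reported as a worsening of a pre-existing condition or of a pre-dose SAE, from first dose to 7 days after last dose.
- State that a matching preferred term in medical history or in a pre-dose SAE does not disqualify such a record.
- State that an AE that starts on treatment and later worsens stays one TEAE at its maximum intensity.
- Keep an event-level exclusion for SAE records known to have started before first dose and not reported as worsened. This is needed because SAP 4.9.1.4 moves a partial start date that falls before first dose to the first-dose date. Without the exclusion, a pre-dose SAE with a missing day could become a TEAE. The dates on which the event met SAE criteria and the investigator became aware of it, both collected under Protocol 8.3.2, can help to identify these records.
- Date a worsening by the start date of the record that reports it, since Protocol 8.3.2 lists no worsening date. List any pre-dose SAE whose worsening has no record of its own.
- State in the CSR if the interim tables used the narrower rule.

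The cost is one paragraph and one derivation flag, using dates already collected and needing no pre-treatment severity grade. TEAE counts will be slightly higher and not directly comparable with the interim. A pre-dose SAE whose worsening has no separate record will still appear only in the listing.
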